Design Overview. This study will be completed as a 6-day inpatient protocol on the Johns Hopkins Hospital and/or Bayview Clinical Research Units (CRU). The sequence and timing of study procedures is shown below. Male (accrual n=12) and female (accrual n=12) participants will be randomized to receive intranasal OT (40 IU/dose) or placebo three times daily. During the CRU stay, participants will complete self-report assessments of alcohol craving, anxiety and depression; nursing staff will administer the CIWA-Ar to evaluate withdrawal symptom severity. Full descriptions for OT administration and assessment instruments are below. During the first 3 days, participants will undergo alcohol abstinence during which 24-hr urinary free cortisol (UFC) will be collected for the first 48 hours. Participants will then complete 3 laboratory procedures in fixed order. A urine toxicology screen, a breath alcohol test, and urine pregnancy test (women) are completed prior to all procedures. Subjects will be terminated from this protocol if they have positive drug toxicology tests (excluding THC) or a positive pregnancy test (females). On procedure days, subjects receive a calorie-controlled breakfast and lunch to control for dietary effects on alcohol absorption or stress response. On day 4, a Trier Social Stress Test (TSST), which includes performance of mental arithmetic and public speaking, will be used to examine subjective and physiological responses to stress. On day 5, an Alcohol Motivated Responding (AMR) procedure, in which subjects respond on the computer to earn either drinks or money and then have the opportunity to self-administer earned drinks, will be used to determine OT effects on motivation to drink and alcohol self-administration. On day 6, a Cumulative Alcohol Dosing (CAD) procedure will be used to examine physiological and subjective responses to fixed-dose alcohol administration. The TSST, AMR and CAD laboratory sessions will start at 1 pm, 30 min after the mid-day OT or placebo administration since OT reaches peak levels in plasma 30-40 min after intranasal administration^[76-78]. On day 7, subjects will have a brief intervention for their hazardous drinking before discharge.

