Subjects who smoke cigarettes or other tobacco products will not be allowed to smoke at any time during the JHH CRU stay. Current smokers on the JHH CRU will be provided with a transdermal nicotine patch (21 mg) at admission and each morning to prevent the onset of nicotine withdrawal; smokers will be patched throughout their JHH CRU stay. Participants residing on the Bayview CRU will be allowed to smoke ad lib in the designated smoking room in the facility. Cigarettes will be held at the nursing station to prevent unauthorized smoking in the participant's bedroom. They will have the option to receive a transdermal patch (21 mg) on the days that they are transported to the JHH campus to complete study procedures.

All session procedures (TSST, ARM and CAD) will be completed in our research office (550 Building). Subjects staying at the JHH CRU will transfer to the Bayview CRU after the TSST for

the remainder of the study. Subjects will be transported via car service to the 550 Building for sessions, then return to the Bayview CRU. The sequence of conditions is:

- Day 1: Admission to Bayview CRU (or JHH CRU)*
** Subjects will be only be admitted to JHH Bayview if they meet defined parameters (see definition below)*
- Days 1-6: Intranasal self-administration of OT (40IU/dose) or placebo three times daily under nursing supervision.
Completion of daily self-report measures three times daily
- Days 1 - 2: Monitored alcohol abstinence
Staff administered CIWA-Ar every four hours while awake*
24-hr collection of urinary free cortisol
Practice AMR session procedures
** symptom triggered benzodiazepine treatment (see below)*
- Day 4: Session 1: Trier social stress test (TSST)
** JHH CRU participants transfer to the Bayview CRU (after TSST session) for the remainder of the study*
- Day 5: Session 2: Alcohol motivated responding (ARM) procedure
- Day 6: Session 3: Cumulative alcohol dosing (CAD) procedure
- Day 7: Brief Intervention for heavy drinking and CRU discharge

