pressure greater than 105, atenolol 25 mg bid will be initiated. For all participants, the Clinical Institute Withdrawal Assessment Alcohol Revised (CIWA-Ar)^[70], which includes 10-items (nausea/vomiting, tremor, paroxysmal sweats, anxiety, agitation, tactile disturbances, auditory disturbances and visual disturbances) will be completed every 4 hours during waking hours. This well validated clinical tool is administered by a nurse, to assess severity of withdrawal symptoms during detoxification, and is the gold standard to direct use of benzodiazepine medication^[79, 80]. CIWA-Ar scores of 8 points or fewer correspond to mild withdrawal, scores of 9 to 15 points correspond to moderate withdrawal, and scores of greater than 15 points correspond to severe withdrawal symptoms. The benzodiazepine lorazepam will be administered as needed using the symptom-triggered method^[80-82]. Specifically, if CIWA-Ar score is ≥ 12 the subject is given a 2mg dose of lorazepam intravenously (IV), the study physician is notified, and CIWA-Ar scores are then repeated 1 hour later. If the score remains ≥ 10 then another 2 mg dose of lorazepam is given. Hourly CIWA-Ar scores and lorazepam treatment are repeated until CIWA-Ar score decreases to less than 9 or until a maximum of 4 doses of 2 mg lorazepam are administered; if CIWA is 9 or higher after 4 doses, subject will be removed from the study. Subjects will also be removed from the protocol for seizures, hallucinations, or disorientation. At that point in time, the physician on call will be contacted who will arrange for transfer to the medical service. The subject is now terminated from the study. Individuals who require benzodiazepine treatment and are successfully treated with lorazepam will remain in the study to complete the 3-day abstinence period, and then will be discontinued from further participation to avoid potential complications and confounds of treatment with benzodiazepines. Discontinued subjects would complete the brief intervention prior to early discharge.

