Ethyl Alcohol/Alcohol: Alcoholic beverages are legally sold to adults. The dose of alcohol used in the CAD was selected to bring blood ethanol levels to approximately 0.1% was determined based on our previous studies and a comprehensive literature on administering alcohol to research subjects. This BAC corresponds to about 1 g/kg alcohol. The drink is prepared by IDS using 190 Proof ethanol (95%v/v, 0.775 g/ml Spectrum Chemical); the total alcohol dose is divided over three drinks, prepared by mixing the appropriate amount of pure ethanol with a sweet beverage. Using standardized drinking units, 1 (e.g. (One standard drink is equivalent to 12 ounces of beer, 5 ounces of wine, or 1.5 ounces of 80-proof spirits.), this amount is about 4-5 drinks for men and about 3-4 drinks for women when consumed in over 2-hour drinking episode. This amount is within the limits of the typical drinking episode of participants, and are not expected to produce significant adverse events.

After the AMR, subjects may consume up to up to 5 standard drinks (70g ethyl alcohol) of an alcoholic beverage of their choice (e.g., beer, wine or liquor) during the alcohol self-administration session, and drinking is paced. These amounts are within the limits of the typical drinking episode of participants and also are sufficiently large to promote alcohol-motivated responding.

Use of intranasal OT and alcohol will be under FDA-approval via IND 110,562 (holder [name], Co-I, *amendment submitted to FDA 8/4/14*). Amendment application is uploaded to eIRB protocol.

Nicotine Patch: Active nicotine patch (21 mg) is the standard of care for management of nicotine withdrawal.

b. Justification and safety information if FDA approved drugs will be administered for non-FDA approved indications or if doses or routes of administration or participant populations are changed.

n/a

c. Justification and safety information if non-FDA approved drugs without an IND will be administered.

n/a/

7. Study Statistics

a. Primary Outcome variables:

- Peak scores for CIWA-Ar and Craving Scales for abstinence days 1-3.
- Total and subscale scores on POMs Short at assessment and during the CRU stay
- UFC for abstinence days 1-3
- Peak salivary CORT in the TSST
- Number of drinks earned in the AMR
- Peak drug effect VAS scores and peak increase in heart beats per minute (bpm) in the CAD

b. Secondary Outcome variables:

- Stimulation and sedation subscales of the BAES in the CAD

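### The day-by-day schedule puts CIWA-Ar scoring and withdrawal monitoring on Days 1-2 only, although abstinence lasts three days and the primary peak CIWA-Ar covers days 1-3

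*Protocol*

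**What the plan says.** The Design Overview in Protocol Section 4.a sends the reader to the list for timing: "The sequence and timing of study procedures is shown below". In that list, the entry "Days 1 - 2: Monitored alcohol abstinence" contains "Staff administered CIWA-Ar every four hours while awake", the 24-hour urine cortisol collection and practice for the alcohol motivated responding task. A note on symptom-triggered benzodiazepine treatment is attached to it and refers to the text that follows. The next dated entry is Day 4, the Trier Social Stress Test. The Days 1-6 entry also covers Day 3, but holds only nasal dosing and "Completion of daily self-report measures three times daily".

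Other parts of the protocol give a longer window:

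- Section 4.a, Design Overview: "During the first 3 days, participants will undergo alcohol abstinence". The same paragraph has "During the CRU stay, participants will complete self-report assessments of alcohol craving, anxiety and depression; nursing staff will administer the CIWA-Ar".
- Section 4.a, Alcohol abstinence: the CIWA-Ar "will be completed every 4 hours during waking hours", with no limit in days. Participants successfully treated with lorazepam finish a three-day abstinence period and then stop.
- Section 7.a, first primary outcome: "Peak scores for CIWA-Ar and Craving Scales for abstinence days 1-3".
- Section 7.d and Section 8.b: a three-day withdrawal phase or period.
- Section 8.a, lorazepam: treated participants whose symptoms are controlled stay for withdrawal monitoring, and their participation ends on day 4.

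**The concern.** The list is what the protocol offers as its timetable, and it places every withdrawal procedure on two days while the outcome and the abstinence period run for three. Two things depend on Day 3 scores.

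The first is the primary outcome. A peak is a maximum, so leaving out a day can only leave it unchanged or lower it. A participant whose highest CIWA-Ar score falls on Day 3 would have an outcome that is not the one defined in Section 7.a.

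The second is the treatment rule. A CIWA-Ar score of 12 or more triggers lorazepam, and anyone given lorazepam does not go on to the laboratory sessions. Day 3 is the last day before the stress test. Section 4.a expects most participants to stay at the Bayview unit, which is mainly domiciliary with nursing care, so scheduled nurse scoring carries some weight there.

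**Working it through.** The protocol gives no figure to reproduce here. The check is a comparison of texts, followed by a count.

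**Step 1. Which days does each source cover for CIWA-Ar and withdrawal monitoring?**

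| Source | Days covered |
|---|---|
| 4.a, sequence of conditions | 1-2 |
| 4.a, Design Overview, abstinence | first 3 days |
| 4.a, Design Overview, CIWA-Ar | the unit stay, so Day 3 is included |
| 4.a, Alcohol abstinence | 4-hourly scoring, no end day; the period is 3 days |
| 7.a, primary peak CIWA-Ar | 1-3 |
| 7.d, withdrawal phase | 3 days |
| 8.a, lorazepam | monitoring, with participation ending on day 4 |
| 8.b, withdrawal | 4-hourly scoring, no end day; the period is 3 days |

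Only the list stops at Day 2. A likely reason is that abstinence monitoring was grouped with the 48-hour urine collection, which does belong on Days 1-2. That is inference; the document does not say so.

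**Step 2. Share of the outcome window with no CIWA-Ar entry in the list.** (3 - 2)/3 = 1/3, or 33% of the days. This counts scheduled days, not lost data. For comparison, craving self-reports within the same outcome are scheduled 3 per day x 3 days = 9 times.

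**Step 3. Number of scores.** Waking hours are not stated, so 14 to 18 are assumed. At four-hour spacing with a score on waking, the daily number is floor(hours/4) + 1:

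- 14 hours: floor(3.5) + 1 = 4
- 18 hours: floor(4.5) + 1 = 5

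Over two days this gives 2 x 4 = 8 to 2 x 5 = 10 scores. Over three days it gives 3 x 4 = 12 to 3 x 5 = 15. Both totals assume a full Day 1. No admission time is given, so Day 1 may hold fewer.

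**Step 4. Effect on the peak.** For each participant, the maximum over Days 1-3 is at least the maximum over Days 1-2. The two differ only if the Day 3 maximum is the highest. The protocol gives no distribution of the day on which CIWA-Ar peaks, so the mean difference cannot be calculated.

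**Step 5. Scale of the safety part.** Section 8.b reports that over 98% of similar participants completed withdrawal without medication that required ending the protocol. If that rate applies here, fewer than (1 - 0.98) x 24 = 0.48 of 24 participants would be expected to need it over the whole withdrawal. The number on Day 3 alone can be no larger.

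**The case against.** The strongest defence is that the operative text already covers Day 3. The four-hourly rule applies to all participants and stands under a heading on an abstinence period that the protocol puts at three days. Section 8.b repeats the rule without a day limit. Section 8.a has lorazepam-treated participants monitored, with participation ending on day 4. The list's benzodiazepine note defers to the narrative, and nothing in the list says that scoring stops after Day 2. Section 7.a also ties CIWA-Ar to days 1-3, so the list is not the only place that links the scale to numbered days. All of this stands and makes the intended window clear. It does not remove the contradiction: the protocol points to the list for timing, and neither narrative rule names an end day.

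Three stronger readings are tempting, and the document does not support them.

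- A reader might infer that Day 3 is missing from the schedule altogether. It is not: the Days 1-6 entry covers dosing and self-reports, so craving is measured on all three days.
- A reader might infer that the primary CIWA-Ar result will be biased or underpowered. Nothing shows that Day 3 scores would in fact be omitted or that omission would differ by arm. The timing evidence in Section 7.c concerns day 1; it does not exclude a later peak, but nothing in the document suggests one.
- A reader might infer that participants are unprotected on Day 3. Lorazepam on physician advice, and removal for seizures, hallucinations or disorientation, apply regardless of the list. Section 5.b also excludes people with a history of serious withdrawal.

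The Design Overview's reference to CIWA-Ar during the unit stay is weak support. Taken literally, it would also require scoring on the session days.

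**Conclusion.** The contradiction is real and stands in the current text. The list schedules withdrawal monitoring, CIWA-Ar scoring and symptom-triggered treatment on two days, against a three-day abstinence period and a primary outcome over days 1-3. The list is the part that is wrong.

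The risk is that a unit following it literally could, not necessarily would, leave one of the three outcome days without CIWA-Ar scores: 8-10 scheduled instead of 12-15, under the waking-hours assumption and a full Day 1. The scheduled trigger for lorazepam on the day before the stress test would be lost with them. The size of any effect on the peak is undetermined, and the safety part appears small. The textual mismatch is certain; an effect on the results is only possible. It is worth correcting because a primary outcome and a treatment trigger depend on the line and the repair costs almost nothing.

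**What to change.** In the sequence of conditions in Section 4.a, change the entry for monitored abstinence, CIWA-Ar and symptom-triggered treatment to Days 1-3. Give the 48-hour urine cortisol collection its own Days 1-2 line; the task practice in the same entry can stay there. In the Alcohol abstinence paragraph of Section 4.a and the withdrawal paragraph of Section 8.b, state that four-hourly CIWA-Ar scoring continues through Day 3.

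If Day 3 is already scored as the narrative directs, the cost is protocol wording only. If not, it is at most about 4-5 additional nurse-administered scores per participant, or 24 x 4 = 96 to 24 x 5 = 120 over the trial, by staff already on the unit. Sample size and analysis do not change.

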The outcome variables for each Aim are listed above. They are all continuous measures. We will first exam the normality by plotting histograms and Shapiro-Wilks tests. The need for transformations and/or use of non-parametric analysis will be determined. In each aim, we compare the outcomes between two groups (OT vs. Placebo), so the statistical analyses will be similar across aims. We will run two-sample t-tests or a non-parametric equivalent method to test if the outcomes are different between the OT-treated and placebo-treated groups. Randomized treatment groups were matched for age, gender and FNDT score; we will evaluate for possible unbalance between the two groups for other baseline measures (e.g., AUD, drinking severity). For each outcome variable, we will construct an ANCOVA model. Potential confounding factors (e.g., gender, mean drinks/week) will be added as covariates to the models, based on sensitivity analysis. We will also complete exploratory analyses of the effects other assessment instruments and alcohol measures (secondary outcome measures) on treatment outcomes.

d. Early stopping rules.

Participants with significant alcohol withdrawal symptoms as indicated by a CIWA-Ar score ≥ 12 , will be treated with benzodiazepines. Individuals who require 4 lorazepam doses (2mg) in and do not show improvement in symptoms (CIWA= 9 or higher) will be removed from the study. Subjects will also be removed from the protocol for seizures, hallucinations, or disorientation. Other individuals in need of benzodiazepine treatment or upon physician recommendation will end participation after completion of the 3-day withdrawal phase; subjects will be discharged pending approval of a physician on day 4 and will not complete the laboratory sessions. Subjects also may be terminated from this protocol if they do not comply with CRU rules or study procedures. They will first be warned of possible dismissal and, if noncompliance persists, will be terminated from the protocol.

Subjects will also be discontinued from the protocol for positive pregnancy test (females) or positive drug toxicology tests (excluding THC).

8. Risks

a. Medical risks, listing all procedures, their major and minor risks and expected frequency.

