using the system triggered method, and additional monitoring of symptoms. A maximum of 4 doses (2 mg IV) will be administered. Lorazepam has been approved by the Food and Drug Administration for treating alcohol withdrawal in this manner. The most common side effects of lorazepam are drowsiness, fatigue and ataxia (decreased muscle control). Other less common side effects include: confusion, depression, headache, hypoactivity, slurred speech, feeling light-headed or dizzy, constipation, nausea, incontinence, changes in libido, urinary retention, slower pulse, cardiovascular problems, low blood pressure, blurred vision or other visual disturbances, blood clots and skin rash. Participants who receive lorazepam will stay in the study to complete alcohol abstinence and withdrawal monitoring only if symptoms are controlled (CIWA < 9), but will not complete the laboratory sessions; participation will end on day 4 of the CRU stay.

- vi. *Nicotine Patch:* Nicotine dependent subjects will be administered a nicotine patch at the time of JHH CRU admission and every morning for the duration of the study. The nicotine patch dose selected for study in this protocol is FDA-approved and has been shown to have a low incidence rate of serious side-effects or adverse events in clinical trials with nicotine-dependent patients. Less than 5% of smokers have to stop using a nicotine replacement product because of side effects. Side effects of nicotine patches may include: skin rash at the location of the patch; sleep problems when using a 24-hour patch, such as having trouble sleeping or having especially vivid dreams. On rare occasions, there have been reports of severe allergic reactions (rash; hives; itching; difficulty breathing; tightness in the chest; swelling of the mouth, face, lips, or tongue); fast or irregular heartbeat; mouth, teeth, or jaw problems; pounding in the chest; severe diarrhea, dizziness, nausea, vomiting, or weakness.

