Participants that have elevated blood pressure that are above safe limits, will be given atenolol . We will initiate system-triggered lorazepam treatment for alcohol withdrawal symptoms if the withdrawal score exceeds the clinical cutoff of CIWA-Ar ≥ 12 or on the advice of the study physician. If the CIWA-Ar score is ≥ 12 the subject is given a 2mg dose of lorazepam, and CIWA-Ar scores are then repeated 1 hour later. If the score remains ≥ 10 then another 2 mg dose of lorazepam is given. Hourly CIWA-Ar scores and lorazepam treatment are repeated until CIWA-Ar score decreases to less than 9 or until a maximum of 4 doses of 2 mg lorazepam are administered; if CIWA is 9 or higher after 4 doses, subject will be removed from the study. Subjects will also be removed from the protocol for seizures, hallucinations, or disorientation. At that point in time, the physician on call will be contacted who will arrange for transfer to the medical service. Individuals who require benzodiazepine treatment and are successfully treated with lorazepam will remain in the study to complete the 3-day withdrawal period, but will not complete laboratory session in order to avoid potential complications and confounds of treatment with benzodiazepines.

To date, we have successfully withdrawn over 98% of our alcohol-dependent subjects without medications requiring protocol termination in studies using a similar population. Exclusion of subjects with a history of alcohol withdrawal complications, and/or high CIWA-Ar scores is a successful strategy to help ensure subject safety in studies of new medications^[118-120].

- v. *Oxytocin administration:* Oxytocin (40 IU/ml, Syntocinon spray, Novartis) and placebo (containing the carrier without the neuropeptide) in identical metered-dose nasal spray bottles (Lukas-Bottles, 5-mL, 0.1 mL/actuation) will be obtained from Pharmaworld, Zurich, Switzerland. Oxytocin will be used in these studies under FDA-approval via IND 110,562. The IND 110,562 is held by our collaborator [name]. This supplier and formulation has been used by [name] in her prior studies. Full information sheets of the nasal spray formulation are uploaded. Oxytocin and placebo will be dispensed by The Johns Hopkins Investigational Drug Services. Throughout the study, subjects will remain on the inpatient CRU, and will complete medication side-effects questionnaires. Forms are reviewed by nurses and study staff.

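### At a CIWA-Ar re-score of exactly 9 after one to three lorazepam doses, the protocol does not settle whether to dose again or whether the subject stays in the study

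*Protocol*

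**What the plan says.** Section 4.a (Alcohol abstinence) describes symptom-triggered lorazepam, and section 8.b (medically supervised withdrawal) repeats the sequence.

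- First dose (4.a): "if CIWA-Ar score is ≥ 12 the subject is given a 2mg dose of lorazepam intravenously (IV"), with a repeat score one hour later.
- Re-dose (4.a and 8.b): "If the score remains ≥ 10 then another 2 mg dose of lorazepam is given".
- Continuation (4.a and 8.b): "Hourly CIWA-Ar scores and lorazepam treatment are repeated until CIWA-Ar score decreases to less than 9 or until a maximum of 4 doses".
- Removal (4.a and 8.b): "if CIWA is 9 or higher after 4 doses, subject will be removed from the study". Section 7.d (Early stopping rules) agrees: subjects who need four doses and "do not show improvement in symptoms (CIWA= 9 or higher) will be removed from the study".
- Retention (8.a, Lorazepam): treated subjects stay to "complete alcohol abstinence and withdrawal monitoring only if symptoms are controlled (CIWA < 9"), and do not go on to the laboratory sessions.
- Remaining treated subjects (7.d): others who need a benzodiazepine finish the 3-day withdrawal phase and then leave. No score is attached to this sentence.

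Section 4.a also classes scores of 8 or fewer as mild withdrawal and 9 to 15 as moderate.

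**The concern.** The re-dose sentence acts from 10 upward, and the continuation sentence stops below 9. CIWA-Ar re-scores are treated here as whole numbers, so one value, 9, lies between the two. A subject who improves from 12 or more to 9 has not reached the point at which treatment ends, yet does not meet the only stated condition for a further dose.

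This is a bedside rule for repeated intravenous lorazepam, applied from nurse-administered scores. Two nurses following the same text could treat the same subject differently. The choice also affects study status, because the number of doses given determines whether the four-dose removal rule can ever apply. The outcomes exposed are those collected during abstinence on days 1-3, which section 7.a lists among the primary outcomes.

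**Working it through.** The protocol gives no figure to reproduce here, so the check sets the written rules side by side.

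**Inputs.** First dose at 12 or more (4.a, 8.b). Re-dose at 10 or more (4.a, 8.b). Repeat until below 9 or four doses (4.a, 8.b). Remove at 9 or higher after four doses (4.a, 7.d, 8.b). Retain through abstinence if below 9 (8.a). Each dose is 2 mg.

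**Step 1: apply each rule to each hourly re-score.**

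| Doses so far | Re-score | Dose under the 10-or-more sentence? | Dose if treatment continues until below 9? | Disposition |
|---|---|---|---|---|
| 1, 2 or 3 | 8 or less | No | No | Retained to end of abstinence phase |
| 1, 2 or 3 | 9 | No | Yes | Not settled |
| 1, 2 or 3 | 10 or more | Yes | Yes | Treatment continues |
| 4 | 8 or less | No | No | Retained to end of abstinence phase |
| 4 | 9 or more | No | No | Removed |

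The two sentences part at one score only, in three dose states.

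**Step 2: follow a subject whose re-score stays at 9 after the first dose.**

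- If the 10-or-more sentence governs, no further dose is given. The total is 1 × 2 mg = 2 mg. The score never falls below 9 and the dose count never reaches four, so neither end condition is met.
- If treatment continues until below 9, re-scores of 9 at three consecutive hours lead to doses two, three and four. The total is 4 × 2 mg = 8 mg, and a fourth re-score of 9 leads to removal.

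**Step 3: disposition on the first path.** Section 8.a does not retain the subject, because 9 is not below 9. Sections 4.a, 7.d and 8.b do not remove the subject for non-response, because four doses have not been given. Read as a catch-all, the 7.d sentence on other treated subjects keeps the subject through the 3-day phase, which differs from the condition in 8.a.

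**Step 4: which outcomes can be affected.** Every lorazepam-treated subject leaves before the TSST, AMR and CAD sessions, so the Aim 2 to 4 laboratory outcomes do not depend on how a 9 is handled. For Aim 1, the CIWA-Ar outcome is the peak score over days 1-3. A score-triggered subject has already reached at least 12, so treatment of a later 9 cannot lower that peak. What remains is later craving, POMS or urinary cortisol data on days 1-3.

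**The case against.** The strongest reply is that the sentences can be read together. In a symptom-triggered scheme, what is repeated each hour may be the whole step: score, then dose only if the threshold is met. On that reading a 9 means keep scoring without a dose, dose again at 10 or more, and stop below 9. A re-dose threshold set above the stop threshold is not incoherent in itself.

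This reading is fair, and it defeats the stronger inference that the protocol gives flatly opposite instructions. It does not close the gap. The continuation sentence names lorazepam treatment as well as scoring among the things repeated, so the other reading stays open. On the harmonised reading, a score that stays at 9 remains in a loop that neither end condition closes.

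A second reply is that the state is usually brief and is supervised. A subject leaves it on reaching 8 or 10. The study physician is notified at the first dose (4.a), lorazepam may be started on the physician's advice (8.b), and participation may be ended on physician recommendation (7.d) or for safety (the removal criteria in section 4). These provisions reduce the practical risk but do not say what the written rule requires at 9.

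A reader might also infer that retention and removal are undefined generally. They are not: retention below 9, and removal at 9 or higher after four doses, are stated consistently.

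**Conclusion.** The point holds for one state only: a re-score of exactly 9 after one, two or three doses. There the protocol does not settle whether another dose is given. If none is given and the score stays at 9, the sections on retention, removal and remaining treated subjects do not yield one disposition. The extreme difference for one subject is 2 mg with no clear status against 8 mg and removal, and it requires 9 at each successive hourly score.

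The main weight is on uniform, safe handling during active withdrawal treatment. The statistical effect is small and confined to later days 1-3 craving, POMS or urinary cortisol data in few subjects. The protocol does not say that data from removed subjects are discarded, so even that loss is not certain. The argument about peak CIWA-Ar assumes that the first dose was triggered by score and not by physician advice alone.

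The documents give no rate for this state. A reader might take section 8.b's figure of over 98% withdrawn and compute 1 − 0.98^24 = 0.38 as the chance of meeting the problem among 24 subjects. The text does not support that use. The figure describes medications requiring protocol termination in earlier studies, 2% is only its upper limit, and the result would be the chance of any such subject, not of one re-scored at exactly 9. No frequency is claimed here.

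**What to change.** Reconcile the re-dose and continuation sentences in section 4.a (Alcohol abstinence) and section 8.b, stating whether what is repeated each hour is a dose or the score-then-dose step. Align the disposition wording in section 7.d (remaining treated subjects) and section 8.a (Lorazepam) with them. The test of the revised text is that every possible score after each dose leads to exactly one action and one study disposition, and that all four places say the same. The clinical team sets the values; none is proposed here.

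The cost is a wording amendment in four places, with no change to sample size, outcomes or analysis.
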